6.3.3. Completer Population

The completer population will include all participants in mITT who were not found ineligible after enrollment, remained enrolled at discharge, have clinician recommended CMV monitoring test interval(s) available and completed the study close-out visit which is scheduled to occur 365 days post-transplant. This population is only being used for sensitivity analyses.

6.3.4. All Enrolled Participants

Some analyses will be completed among all enrolled participants. This includes all randomized participants, if in the randomized cohort, or enrolled, if in the observational cohort.

6.3.5. Safety Population

The safety population will consist of all enrolled participants that had any safety data collected after randomization. Most of the safety data will be collected at the quarterly contact.

6.4. Covariates and Subgroups

As randomization was stratified by transplant site and participant's perceived ease of access to blood draw facility, transplant site and participant's perceived ease of access to blood draw facility are included as covariates in the logistic regression used to conduct the primary analysis.

The protocol does not define any formal subgroup analyses and the study is not adequately powered to perform subgroup analyses. However, a sensitivity analysis will be conducted for the adherence outcome measures to exclude all participants from the University of Minnesota, as this site entered actual number of monitoring tests into the recommended monitoring schedule.

6.5. Missing Data

6.5.1. Withdrawal Prior to First Recommended Monitoring Test

If participants withdraw prior to their first scheduled clinician-recommended CMV monitoring test, the number of recommended clinician-recommended CMV monitoring tests will be zero, monitoring compliance cannot be calculated. These participants will be included in the ITT analyses and considered as fail, not meeting the >90% threshold for the primary endpoint. They will not be included in the mITT or Completer analyses.

If the clinician recommended monitoring test interval is "No further monitoring required" at discharge and not changed until withdrawal or 1 year after HCT, then these participants will be included in the ITT analyses and considered as fail, not meeting the >90% threshold.

6.5.2. Withdrawal After First Recommended Monitoring Test

If participants withdraw after their first scheduled clinician recommended CMV monitoring test the number of clinician recommended CMV monitoring test will not be zero. Therefore, the monitoring compliance can be calculated with the actual number of clinician-recommended CMV monitoring tests completed prior to

withdrawal divided by the number of recommended clinician-recommended CMV monitoring tests before withdrawal.

6.5.3. Missing Participant Questionnaires

In the DBS arm participants were asked to complete satisfaction questionnaires. Since participants have the option to respond "Prefer Not to Answer" for any given question, this answer will be considered as missing for analysis. The number of missing responses will be reported. Composite scores combining responses to multiple survey questions are defined in Section 12.2. For a given composite score, only observations where responses are available for all component survey questions of the score will be used to compute the composite and the number of participants excluded for this descriptive analysis will be reported. Because the composite scores will not be used in analyses of hypothesis tests, advanced methods of imputing missing responses based on assumed data distributions will not be attempted, and descriptive results will be presented with a discussion of the frequency of missing responses for each item.

6.6. Interim Analyses and Data Monitoring

See Section 6.2.1 for a description of interim analyses and interim monitoring.

6.7. Multicenter Studies

Randomization is stratified by transplant site. Transplant site will be included as a covariate in the logistic regression used to conduct the primary analysis.

6.8. Multiple Comparisons/Multiplicity

There is only one primary outcome measure. No adjustments for multiple testing are planned.

7. STUDY PARTICIPANTS

7.1. Disposition of Participants

The disposition of participants in the study will be tabulated by intervention group (Table 5). The table shows the total number of participants screened, enrolled/randomized, early terminated (including those who consented and did not consent to data collection from medical records), remained enrolled at discharge, remained enrolled through the date of the first scheduled clinician-recommended CMV monitoring test, completed at least one scheduled clinician-recommended CMV monitoring test, collected DBS sample with laboratory results, and completed the study close-out visit. Table 7 will summarize the dates of first enrollment by site and intervention group. Table 8 will present a summary of the reasons that participants were screened but not enrolled into the randomized cohort.

The composition of participant analysis populations, including reasons for participant exclusion, by intervention group, is presented in Table 6. Individuals excluded from analysis populations are presented in Listing 4.

A flowchart showing the disposition of study participants, adapted from the Consort Statement will be included (Figure 2). This figure will present the number of participants screened, enrolled, lost to follow-up, and analyzed, by intervention group.

A listing of participants who terminated from study follow-up and the reason will be included in Listing 1.

7.2. Protocol Deviations

A summary of participant-specific protocol deviations will be presented by the reason for the deviation, the deviation category, and intervention group for all participants (Table 3). Deviations will be reviewed by the Sponsor and classified as either major or minor. All participant-specific protocol deviations and non-participant specific protocol deviations will be included in Appendix 3 as data listings (Listing 2 and Listing 3, respectively).

8. ADHERENCE EVALUATION

Descriptive statistics will be reported by intervention group and overall, for the adherence outcomes. N, Mean, Standard Deviation, Minimum and Maximum will be reported for continuous adherence variables and number and percent for categorical adherence variables.

Primary and secondary analyses of adherence outcomes will be performed using logistic regression models. Separate models will be fit to the binary outcome of whether or not individual participants completed >90% of their clinician recommended CMV monitoring, and to the proportion of completed clinician recommended CMV monitoring tests per participant. All models will include intervention and the categorical stratification variables transplant site and participant's perceived ease of access to blood draw facility as independent variables.

Model assumptions will be checked by viewing plots of the residual distribution, and the model will be adjusted accordingly based on the assumption check. Listings of CMV monitoring results (including clinician-recommended and self-collected) and clinician-recommended monitoring intervals will be presented in Listing 9 and Listing 13, respectively.

8.1. Primary Adherence Analysis

A traditional logistic regression model will be fit to the ITT population where the outcome is whether or not the participants completed > 90% of their clinician-recommended CMV monitoring tests in the study period by 1-year after HCT. A two-sided Wald-test for evidence of a non-zero coefficient for intervention group in the regression will be conducted at the 5% significance level. This analysis will be repeated in the mITT population and the Completer population. The summary of the primary adherence analysis results will be presented in Table 14.

A sensitivity analysis, logistic regression will be fit in the ITT and mITT populations with the maximal possible study period, where the outcome is whether or not the participant completed > 90% of their recommended monitoring tests by the end of maximal possible study period. These results will be presented in Table 15.

In addition, as a sensitivity analysis, logistic regression will be fit in the ITT and mITT populations excluding all participants from the University of Minnesota (See Section 6.4), where the outcome is whether or not the participant completed > 90% of their recommended monitoring tests by 1-year after HCT. These results will be presented in Table 16. Example SAS code for this analysis is included below and specifies the INFLUENCE option to display regression diagnostics and the PARAM=REF option to obtain parameter estimates appropriate to the reference coding where the regression coefficient and odds ratio are estimated for the effect of the intervention compared to the standard of care.

ODS GRAPHICS ON;

PROC LOGISTIC DATA=DSN;

CLASS TRT SITE EASE / PARAM=REF;

MODEL SUCCESS = TRT SITE EASE /INFLUENCE IPLOTS;

RUN;

ODS GRAPHICS OFF;

8.2. Secondary Adherence Analyses

A fractional logistic regression model will be fit with quasi-maximum likelihood estimates in the ITT population where the outcome will be the proportion of recommended monitoring tests completed per participant, and the covariates will be randomized intervention group and the stratification variables. This fractional response model was introduced by Papke and Wooldridge (1996) in their frequently cited extension of the generalized linear model to analyze proportion data that are bounded by 0 and 1. Although commonly applied to these outcome data for simplicity, ordinary least squares regression assumes that the predictor variables and continuous outcome variable are linearly related and that the variance is independent of the mean, the violations of which in models of fractional outcomes result in biased estimates and potentially misleading inference. The marginal effects of predictor variables on the mean proportion response can be estimated using the binominal likelihood framework with robust standard errors. Appropriate to the proportion outcome data, the model allows for responses at the 0 and 1 boundaries, in contrast to the beta regression approach that has been described for proportion data that do not include extremes (zero or one).

To estimate the treatment effect of the DBS intervention on the proportion of recommended tests completed by individuals in the DBS vs SOC group, we will fit the fractional logistic model using SAS PROC GLIMMIX with logit link function and the random residual option to estimate model parameters using a quasi-likelihood function. A two-sided Wald-test for evidence of association between intervention group and proportion of recommended monitoring tests completed will be conducted at the 5% significance level. This analysis will be repeated in the mITT population and the Completer population. The results from the models of the proportion of recommended tests completed will be presented in Table 17. Table 18 presents the results from the sensitivity analysis conducted on the ITT and mITT populations with the maximal possible study period. Table 19 presents the results from the sensitivity analysis conducted on the ITT and mITT populations excluding participants from the University of Minnesota. Example SAS code for this analysis is shown below and specifies the S or SOLUTION option to report the fixed effects parameter estimates, and ILINK option to report estimates on the mean (probability) scale. Variables for transplant site and the participants' perceived ease of access to the blood draw facility will be included as covariates as described in Section 8 for all adherence models.

PROC GLIMMIX DATA=DSN;

MODEL PCT=TRT SITE EASE/ DIST=BINOMIAL LINK=LOGIT S;

RANDOM _RESIDUAL_;

OUTPUT OUT=FRACOUT PRED(ILINK)=PRED LCL(ILINK)=LOWER UCL(ILINK)=UPPER; RUN;

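### The example GLIMMIX code for the secondary adherence analysis (SAP 8.2) does not fit the model the SAP describes: site is not declared categorical, and the standard errors are scaled model-based ones, not robust ones.

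*SAP*

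**What the plan says.** SAP 8 sets the rule for every adherence model: "All models will include intervention and the categorical stratification variables transplant site" and perceived ease of access. SAP 8.2 repeats, just before its code, that both enter as Section 8 describes.

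On the variance, 8.2 says two things. It introduces the fractional logit approach by saying that marginal effects "can be estimated using the binominal likelihood framework with robust standard errors". It then states the fitting plan as GLIMMIX with a logit link and "the random residual option to estimate model parameters using a quasi-likelihood function". The test is specified as "A two-sided Wald-test for evidence of association between intervention group and proportion of recommended monitoring tests completed", at the 5% level.

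The example block has a PROC GLIMMIX line with no EMPIRICAL option, the statement "MODEL PCT=TRT SITE EASE/ DIST=BINOMIAL LINK=LOGIT S", and `RANDOM _RESIDUAL_` with no SUBJECT= term. It contains no CLASS statement. The primary-analysis code in 8.1 does have a CLASS statement naming treatment, site and ease.

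**The concern.** The code and the text describe different analyses, and they would give different p-values in Tables 17 to 19.

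**Site.** There are four sites. Without CLASS, a numeric site variable is fitted as a straight line on an arbitrary code, using 1 degree of freedom where 3 are needed. If site is stored as text, the program stops. Treatment and ease have two levels each, so numeric coding fits them equivalently.

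**Variance.** `RANDOM _RESIDUAL_` alone estimates one dispersion factor across both arms and multiplies the model-based variance by it. It is not a sandwich variance. With 100 participants on DBS and 50 on SOC, the common factor is driven mostly by DBS, while the variance of the treatment contrast is driven mostly by SOC. If SOC adherence is the more dispersed, the standard error is too small.

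At stake is a pre-specified 5% test that supports the first secondary objective.

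**Working it through.** **Inputs from the documents.** 150 participants, 100 DBS and 50 SOC (SAP 5); four sites (Protocol 11.3); ease in two levels (SAP 4.4.3); two-sided 5% (SAP 8.2); 26 to 43 weeks on study (SAP 4.1), used here as the number of weekly tests. The documents give no dispersion, site shares or site effects; those are assumed.

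**The plan's own figure.** For the secondary analysis the SAP states only the nominal 5%. Its one design figure is the primary power, which confirms the arm sizes. For 0.80 against 0.50, the pooled proportion is 0.70, so 1.96 × √(0.70 × 0.30 × (1/100 + 1/50)) = 0.156. The unpooled SE is √(0.16/100 + 0.25/50) = 0.0812. Then (0.30 − 0.156)/0.0812 ≈ 1.78, giving 96.2% (stated 96%). The other rows give 88.5% (89%) and 80.4% (80%).

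**Why a common factor misses the level.** Let φ be an arm's dispersion factor. With equal means:
- true variance of the treatment contrast ∝ φ_DBS/100 + φ_SOC/50
- variance with one pooled factor ∝ [(100φ_DBS + 50φ_SOC)/150] × (1/100 + 1/50)
- true ÷ estimated = (φ_DBS + 2φ_SOC)/(2φ_DBS + φ_SOC)

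For a beta-binomial proportion on m tests with intraclass correlation ρ, φ = ρ + (1 − ρ)/m. Take m = 34.5, the midpoint of 26 and 43. With ρ = 0.15 (DBS) and 0.45 (SOC), φ = 0.175 and 0.466. The ratio is 1.107/0.816 = 1.36, so the true SE is 1.165 times the estimated one. The effective critical value is 1.96/1.165 = 1.68, and rejection is about 9.3%.

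**Simulation against that formula.** Null case, 6,000 trials per row, stratified 2:1, 26–43 tests, no site effects; Monte Carlo error about 0.3–0.4 points. Sandwich is the uncorrected form.

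| ρ DBS / SOC | Formula | Code as printed | CLASS only | CLASS + sandwich |
|---|---|---|---|---|
| 0.30 / 0.30 | 5.0% | 4.9% | 5.0% | 5.9% |
| 0.25 / 0.35 | 6.2% | 6.3% | 6.2% | 5.7% |
| 0.15 / 0.45 | 9.3% | 9.4% | 9.4% | 6.0% |
| 0.10 / 0.50 | 11.0% | 10.5% | 10.7% | 5.9% |
| 0.45 / 0.15 | 2.2% | 2.2% | 2.3% | 5.2% |

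A second, separate simulation gave 4.4% (equal), 5.6% (SOC moderately more dispersed), 8.2% (SOC much more) and 2.8% (DBS more) for the printed code, against 5.1–6.3% with CLASS and sandwich errors. In the 6,000-trial runs, small-sample corrections brought the sandwich test to 4.7–5.4% (HC2) or 4.2–5.0% (HC3) over all null scenarios.

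**Effect of the missing CLASS.** With non-monotone site effects and equal dispersion, null rejection is 2.7% with numeric site and 4.5% with CLASS. Site is balanced by the stratified randomization, so unmodelled site variation enlarges the residual scale without enlarging the error of the treatment contrast. In one example with a true log-odds effect of 0.8, power was 83% with numeric site and 88% with CLASS.

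**Both together.** With non-monotone sites and ρ of 0.15 / 0.45, the printed code rejects 5.9%, CLASS alone 9.9%, and CLASS plus sandwich 5.9%. Here the two faults partly cancel, and adding CLASS alone exposes the variance problem.

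**The case against.** **It is only example code, and the text governs.** This is fair as to intent: Section 8 leaves no doubt that site is categorical, and the documents do not say how site is coded. But the block is the only worked specification of this model, and the parallel primary code gets it right. A programmer who runs it as printed gets a wrong adjustment or an error.

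**The SAP does not plainly promise robust errors.** A reader might infer that the code breaks a firm commitment. It does not go that far. The sentence on robust errors is background and says what can be done; the fitting sentence names the random residual option, which the code uses. The variance mismatch is therefore softer than the CLASS mismatch. What stands is that 8.2 describes one variance and codes another without saying which feeds the Wald test.

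**Residual plots will be checked and the model adjusted.** SAP 8 says so, but names no variance estimator to fall back on. Choosing one after seeing the data is what pre-specification should avoid.

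**Unequal dispersion is an assumption.** True. Completed tests in both arms come from the same chart-review form (SAP 3.3.5), and nothing in the documents says SOC will be more variable. That is why the size is given as a range in both directions.

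**Conclusion.** The mismatch is real on both counts. The missing CLASS statement contradicts Section 8 and the primary code; it is neutral to conservative for type I error and can lose power. The variance in the code keeps the 5% level only if the arms are about equally dispersed. Under the assumed scenarios rejection is about 5% (equal), 6% (SOC moderately more dispersed), 8–10% (SOC much more) or 2–3% (DBS more). With both corrections it is about 5–6% throughout. These figures rest on assumed beta-binomial dispersion, site shares and site effects.

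Three stronger readings are not supported. A reader might infer that both omissions inflate the error rate; only the variance can, and the missing CLASS works the other way. A reader might infer that the test is anti-conservative in general; the documents give no dispersion figures, and the direction depends on which arm varies more. A reader might also infer that linear site biases the treatment effect, since one simulation with a true log-odds effect of 0.60 averaged 0.56 with numeric site and 0.60 with CLASS. Averaging its site logits (0, −1.2, 0.8, −0.6) over equal sites gives a marginal log-odds ratio of 0.53–0.56 for intercepts 0 to 1.5, with perfect balance. A drop of that size is expected from the non-collapsibility of the odds ratio and is not shown to be bias.

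The point concerns the secondary p-value. The primary logistic analysis is not affected, and Tables 18 and 19 define their intervals as mean ± 1.96 SE without tying them to this model.

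**What to change.** Change the example code in SAP 8.2 as follows, leaving the MODEL statement as it is:
- `PROC GLIMMIX DATA=DSN EMPIRICAL;`, preferably with one of its small-sample corrections
- `CLASS ID TRT SITE EASE;` with SOC set as the reference level of TRT
- `RANDOM _RESIDUAL_ / SUBJECT=ID;`

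Add one sentence to the text saying that the Wald test uses the robust (sandwich) standard error, and name the correction. Make all the changes together, because CLASS alone does not restore the 5% level.

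The cost is a few lines. The standard error may be larger when SOC is the more dispersed arm. In one simulation of 1,500 null trials (beta precision 6 for DBS, 1.2 for SOC, CLASS in the model) the robust SE was 0.225 against a model-based 0.194. That is 0.225/0.194 = 1.16, or 16% larger, and close to the actual sampling SD of 0.230. Without a small-sample correction, the sandwich test can run slightly above 5% at this sample size.

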8.3. Exploratory Adherence Analyses

No exploratory adherence analyses are planned.

9. SAFETY EVALUATION

9.1. Demographic and Other Baseline Characteristics

Summaries of age, sex, ethnicity, race, transplant site, participants' perceived ease of access to blood draw facility, and days from HCT (calculated as the time from enrollment – HCT date + 1) will be presented by intervention group in Table 11 and Table 12. Similar summaries of categorical and continuous demographic and baseline characteristics will also be presented by site for the randomized cohort (Table 9 and Table 10). Ethnicity is categorized as Hispanic or Latino, or not Hispanic and not Latino. In accordance with NIH reporting policy, participants may self-designate as belonging to more than one race or may refuse to identify a race, the latter reflected in the CRF as "No" to each racial option.

Individual participant listings (Appendix 3) will be presented for all demographics (Listing 5) sorted by intervention group, and Participant ID.

9.1.1. Prior and Concurrent Medical Conditions

A summary of transplant and neoplastic disease characteristics is presented by intervention group in Table 13. Listings of participants' transplant information, GVHD status, and CMV reactivation or disease will be presented (Listing 6, Listing 7, and Listing 8). Proven/Probable CMV disease is considered a Serious Adverse Event of Special Interest and is summarized as described in Section 9.4.

9.1.2. Prior and Concomitant Medications

Concomitant medications will be coded to the Anatomical Therapeutic Classification using the WHO Drug Dictionary. The use of prior and concomitant medications taken during the study will be recorded on the CRFs. A by-participant listing of concomitant medication use will be presented. The use of concomitant medications during the study will be summarized by ATC1, ATC2 code and intervention group for the Safety population (Table 30).

9.2. Adverse Events

When calculating the incidence of adverse events (i.e., on a per participant basis), each participant will only be counted once and any repetitions of adverse events within a participant will be ignored; the denominator will be the total population size. All adverse events reported will be included in the summaries and analyses. Overall summary of adverse events (Table 20) and adverse events occurring in more than 5% of participants in any intervention group (Table 21) are summarized. Table 21 presents data by MedDRA system organ class, preferred term, and intervention group.

9.2.1. Elicited Events

The number and proportion of participants in the DBS arm experiencing Finger-Stick Procedure-Related Severe Adverse Events will be presented (Table 24). The exact 95% binomial CI for the proportion of participants and the total number of events will also be presented.

9.3. Deaths, Serious Adverse Events and other Significant Adverse Events

Proven or probable CMV disease is a serious adverse event of special interest. The number of participants, proportion of participants and Clopper-Pearson Exact 95% confidence interval for all enrolled participants experiencing proven or probable CMV disease between discharge and 365 days after HCT will be

summarized in the randomized groups (Table 22). The same quantities will be summarized between HCT and 365 days after HCT in the randomized groups (Table 23).

To assess whether incidence of possible, probable or proven CMV disease at 1 year differed between intervention groups, the proportional hazards model for the sub distribution of CMV (ShafeFine and Gray, 1999) with death as a competing risk will be fit in the safety population. Example SAS code for this analysis is included below and specifies the EVENTCODE=1 indicate the event of interest is relapse of CMV (status =1), death is the competing risk (status =2), and censored observations are those with Status = 0. The PLOTS =CIF option to obtain cumulative incidence function of each intervention group.

DATA RISK;

TRT=1; OUTPUT;

TRT=2; OUTPUT;

FORMAT TRT TRTGRP;

PROC PHREG DATA=DATA PLOTS (OVERLAY=STRATUM)=CIF;

CLASS TRT (ORDER=INTERNAL REF=FIRST);

MODEL T*STATUS(0)= TRT / EVENTCODE=1;

HAZARDRATIO TRT/DIFF;

```
BASELINE COVARIATES=RISK OUT=OUT1 CIF=_ALL_ / SEED=SEED;
```

RUN;

The outcome of the regression will be the occurrence of possible, probable or proven CMV disease. End of follow-up will be defined as the earliest of death date, date of withdrawal, or 365 days post HCT. Gray's test will be used to test for differences in the sub distribution hazard of CMV disease between intervention groups at the 5% significance level, the cumulative incidence function of CMV diseases presented (Figure 3).

Similarly, for another analysis with all enrolled participants, the proportional hazards model for the sub distribution of CMV disease, with death as a competing risk, will be fit. Gray's test will be used to test for differences in the sub distribution hazard of CMV disease between the All Randomized and Observational groups at the 5% significance level, the cumulative incidence function of CMV diseases presented (Figure 4).

The following listings describing deaths, SAEs, or other significant AEs will be presented:

- Serious Adverse Events of Special Interest (Table 25);
- Finger-Stick Procedure-Related Severe Adverse Events (Table 26);
- Unanticipated Adverse Device Effects (Table 27);
- Deaths (Table 28);
- Hospitalizations (Table 29).

